#### Table 4: Expansion Phase Disease Response and Follow-up Assessments

				Cycle	/ Day		-			
			Cycle 1		Сус	le 3	Cycle 5 and then every 2 cycles 	End of Treatment (EOT) 	PD Follow- up 	Survival Follow- up 
Procedure 	Screening D-30 to -1	D1	D8 ± 3	D15 ± 3	D1 ± 3	D15 ± 3	D1 ± 4	≤7 d from last dose	Q2M (± 1M)	Q3M (± 1M)
PET-CT or CT or MRI 	X7				X 		X	X	Х	
ECOG performance status	X						X	X	Х	
Survival status										X

Abbreviations: C = cycle; CT = d = day; D = Study Day; ECOG = Eastern Cooperative Oncology Group; EOT = End-of-Treatment; FDG = fluorodeoxyglucose; IRC = independent review committee; M = month; MRI = magnetic resonance imaging; PD = progressive disease; PET = positron emission tomography; PTCL = peripheral T-cell lymphoma; Q2M = every 2 months.

- 1. See Section 6.11 for additional information on disease response assessments.
- 2. Additional visits may be scheduled / procedures may be performed at the Investigator's discretion, as clinically indicated.
- 3. The EOT visit is to be performed within 7 days after the last study drug dose.
- 4. Patients who discontinue treatment from duvelisib for reasons other than PD are to have disease response assessments performed Q2M until the development of PD, as determined by the Investigator, death, or initiation of alternate anti-cancer therapy.
- 5. After development of PD, as determined by the Investigator, patients are to be followed Q3M for survival until closure of the study by the Sponsor; this follow-up may be conducted via telephone.
- 6. PET-CT is the preferred method of assessment. The modality chosen to evaluate response in each individual patient should be the same throughout the duration of the study. PET images are to be assessed using the 5-point scale (5PS). At each scheduled timepoint, the Investigator will be asked to provide a PET-CT-based response, based on the Lugano (Cheson et al. 2014) response criteria. Images will be centrally stored and read, with disease response determined by the IRC using the central image assessments.

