# 4.3. Duration of Patient Participation

The duration of patient participation is dependent on the patient's tolerance of and response to duvelisib; it is anticipated that patients will participate in the study for a minimum of  $\sim$ 3 months.

All patients will be screened for study eligibility within 30 days before the first study drug dose (i.e., Baseline, C1D1). Patients who are determined to be eligible will be enrolled in the study at Baseline and will receive duvelisib continuously in 28-day cycles. For the Dose Optimization Phase, it is anticipated that patients will receive at least 1 cycle of therapy. For the Expansion Phase, it is anticipated that patients will receive at least 2 cycles of therapy. Unlike the Dose Optimization Phase if the patient demonstrates progression and no dose modification was required for toxicity, the patient may re-escalate to 75 mg BID with a confirmatory scan after approximately 4 weeks of therapy. Patients will continue duvelisib until development of PD or intolerance or another discontinuation criterion is met, as determined by the Investigator; no maximum duration of therapy has been set. After discontinuation of duvelisib, all patients are to attend an End-of-Treatment (EOT) visit within 7 days after the last study drug dose and then a Safety Follow-up visit 30 days after the last study drug dose. Patients who have not experienced PD will continue to be followed for disease response as per Table 3 or Table 4 until development

of PD, as determined by the Investigator. Patients with documented PD, as determined by the Investigator, will be followed on an every 3-month basis for survival until closure of the study by the Sponsor; follow-up for survival may be conducted via telephone.

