# 7.1. Completion of Study

Patients will be considered to have completed the study at the time of documented PD or death or closure of the study by the Sponsor.

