5.2.2.4 Overall Survival

OS will be assessed using Kaplan-Meier methods from time of first treatment to death using the same methods described for PFS. Patients without documented death will be censored at last alive date. OS analysis will be repeated for the subset of enrolled Japanese patients.

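### Survival follow-up starts only at investigator-determined PD, so patients who begin new therapy or are transplanted without PD have no scheduled survival contact, and OS may be informatively censored

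*Protocol*

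**What the plan says.** **End of scan follow-up.** Protocol Table 4, footnote 4, has patients who stop duvelisib for a reason other than PD scanned every two months "until the development of PD, as determined by the Investigator, death, or initiation of alternate anti-cancer therapy". Table 3, footnote 4, and footnote 6 of Tables 1 and 2 give the same stopping points.

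**Start of survival follow-up.** The fifth footnote of Table 4 reads: "After development of PD, as determined by the Investigator, patients are to be followed Q3M for survival". In Tables 3 and 4 this contact runs to study closure. Table 3, footnote 5, and footnote 7 of Tables 1 and 2 use the same trigger, and all of them allow contact by telephone. Section 4.3 agrees: "Patients with documented PD, as determined by the Investigator, will be followed on an every 3-month basis for survival". For patients without PD, Section 4.3 mentions disease assessment only: "Patients who have not experienced PD will continue to be followed for disease response as per Table 3 or Table 4".

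**Study completion.** Section 7.1 has this rule: "Patients will be considered to have completed the study at the time of documented PD or death or closure of the study by the Sponsor".

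**Analysis.** OS is a secondary endpoint in both phases (Protocol 3.1.2 and 3.2.2), estimated by Kaplan-Meier from first treatment to death. SAP 5.2.2.4 gives the censoring rule: "Patients without documented death will be censored at last alive date". It has no separate rule or sensitivity analysis for patients who change therapy without PD.

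**The concern.** Read together, the two sets of footnotes leave a gap. New therapy closes the scan schedule but does not open the survival schedule. A patient who goes to transplant in response, or is switched while stable, leaves one schedule and qualifies for no other.

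The plan foresees this path. SAP 5.2.1.1 lists transplant apart from PD as a reason for ending treatment, SAP 4.5.2 makes post-baseline stem cell transplant a prognostic factor, and the PFS censoring table in SAP 5.2.2.3 has a row for new treatment before progression.

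Moving to transplant or another therapy depends on response, tolerance and fitness, all of which plausibly bear on survival. Kaplan-Meier treats a censored patient as having the same later risk as those still followed. If these patients are censored around the time they switch and their later risk differs, the OS curve is biased, and the trial will not hold the data to correct it.

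**Working it through.** **1. Does any other rule close the gap?**

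| Place | What happens to a patient who starts new therapy without PD |
|---|---|
| Tables 1-2 fn 6; Tables 3-4 fn 4 | Scans stop |
| Tables 1-2 fn 7; Tables 3-4 fn 5; Section 4.3 | Survival contact not triggered, because PD has not occurred |
| Section 8.2 | New therapy is not a reason for withdrawal, so the patient stays on study without scheduled contact |
| Section 10.3 | Death must be reported after intervening treatment, but only within the adverse event reporting period (30 days after last dose) |
| SAP 5.2.2.4 | Censored at last alive date |

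No rule sends this patient to three-monthly survival contact. The one remaining route is PD noted later by the investigator. Entry by that route would itself be selective, because it brings in patients whose disease has returned.

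**2. How much could it matter?** The documents give no OS event count, no OS power and no rate of switching, so there is no plan figure to reproduce. What follows is an illustration.

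Inputs:
- Median OS 8.4 months, from the 16 Phase 1 PTCL patients in Protocol 1.2, used here with a constant hazard: λ = ln 2 / 8.4 = 0.0825 per month.
- Assumed: a share q of 5% to 30% is destined for new therapy at a time uniform over months 3 to 6, if still alive. About exp(-0.0825 × 4.5) = 0.69 of them reach the switch, so 3.5% to 21% of all patients switch.
- Assumed: the hazard after the switch is h times that of the others, with h from 0.33 to 2.
- Assumed: every switcher is censored at the switch. This is the worst case.

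Closed form, with the switch placed at its mean of 4.5 months:
- Censored at switch: S(12) = exp(-0.0825 × 12) = 37%, whatever q and h are. The estimate behaves as if switchers kept the others' hazard.
- Followed to death: S(12) = (1 - q) × 0.37 + q × exp(-0.0825 × (4.5 + 7.5h)).
- q = 0.30, h = 0.33: 0.7 × 0.3715 + 0.3 × 0.562 = 43%. Error 37 - 43 = about -6 points.
- q = 0.30, h = 2: 0.7 × 0.3715 + 0.3 × 0.200 = 32%. Error 37 - 32 = +5 points.

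A simulation of 400,000 patients per scenario, with follow-up cut at 36 months, agrees. In each range the first value is for q = 5% and the second for q = 30%:

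| h | Median OS, all followed (months) | 12-month OS, all followed | 12-month OS, censored at switch | Error (points) |
|---|---|---|---|---|
| 0.33 | 8.5 to 9.5 | 38.1% to 43.0% | 37.1% to 37.3% | -1.0 to -5.7 |
| 0.5 | 8.5 to 9.1 | 37.8% to 41.2% | 37.1% to 37.2% | -0.7 to -4.0 |
| 1 | 8.4 | about 37% | about 37% | 0 |
| 2 | 8.2 to 7.6 | 36.4% to 32.1% | 37.2% to 37.3% | +0.8 to +5.2 |

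The censored median is 8.4 months throughout.

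A second set of assumptions has 10% to 20% leaving at months 3 to 6, with median survival of 30 months against 9 for the rest and administrative censoring at 12 to 30 months. It gives 12-month OS of 43.4% to 46.9% with full follow-up and 40.9% to 41.8% with censoring, an error of -2.5 to -5.1 points.

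**3. Comparison with sampling error.** At 100 patients and 37% survival, the simple binomial 95% half-width is 1.96 × √(0.37 × 0.63 / 100) = 9.5 points. The possible bias is smaller than that, but the confidence interval does not reflect it and more patients do not reduce it.

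**4. Section 7.1 against the tables.** Section 7.1 ends a patient's study at PD. Table 4, footnote 5, and Section 4.3 require survival contact from PD until study closure. Both cannot stand, and the completion count reported under Protocol 11.6 and SAP 5.1.1 depends on which is used.

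**The case against.** The strongest case against the point is that its effect is small and uncertain. OS carries no hypothesis, power or comparator in a single-arm phase. The bias rests on assumed rates, vanishes when the hazards are equal, and can take either sign. Nor must every switcher be lost at the switch. The SAP codes systemic therapy given after study treatment (4.8), records post-baseline transplant (4.5.2) and summarises deaths during follow-up (5.3.8), so sites may hold later alive dates. All of this stands, and it limits the claim to what may happen. It does not supply a scheduled contact.

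A reader might infer four stronger things that the documents do not support:
- **That these patients never enter survival follow-up.** The PD trigger has no time limit and does not exclude PD after new therapy.
- **That Section 7.1 itself censors OS.** Patients at PD are the group explicitly followed for survival, and the SAP censors at last alive date, not at study completion. Section 7.1 is a contradictory label that a site could misapply.
- **That Section 4.3 clearly conflicts with the stop at new therapy.** It refers to Tables 3 and 4 and so takes in their footnotes. It is better read as a summary.
- **That a planned OS comparison by transplant is compromised.** SAP 4.5.2 speaks of key efficacy endpoints without naming OS. The sections on ORR and PFS repeat their analyses by those factors, whereas SAP 5.2.2.4 names only the Japanese subset.

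**Conclusion.** The gap is real on the text and no other rule closes it. Followed as written, the plan leaves a group whose selection is plausibly linked to prognosis without scheduled survival contact, so OS may be informatively censored. It cannot be said that it is: that depends on how many patients switch without PD, on their later hazard, and on what sites record unprompted. The range of about -6 to +5 points at 12 months assumes 3.5% to 21% switching at months 3 to 6, a later hazard between one third of and twice the others', and loss of every switcher at the switch. The primary IRC-assessed ORR is not touched. The conflict between Section 7.1 and the survival follow-up rules is a separate matter of wording that should be reconciled. The change is worth making because it is cheap and because analysis alone cannot recover follow-up that was never collected.

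**What to change.** **Protocol.** Reword footnote 7 of Tables 1 and 2, footnote 5 of Tables 3 and 4, and Section 4.3. Every treated patient should enter three-monthly survival follow-up, by telephone if convenient, when disease follow-up ends for any reason, including new anti-cancer therapy, and should stay in it until death, withdrawal of consent or study closure. Align Section 7.1 so that completion is not declared at PD while survival contact is still due.

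**SAP.** In 5.2.2.4, tabulate OS censoring by reason and add a sensitivity analysis for patients who start new therapy or have a transplant without PD, for example by varying their assumed hazard after the switch.

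**If follow-up is already advanced.** The SAP history lists a final version in August 2023, so an amendment may come late. One survival-status sweep of all treated patients before the data cut would recover most of the benefit.

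**Cost.** A wording amendment, one extra table and analysis, and quarterly calls, by a method already in use, for what is probably a minority of patients.

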#### Table 5: Dose Optimization and Expansion Phase Pharmacokinetic Assessment

Abbreviations: AE = adverse event; BID = twice daily; PK = pharmacokinetic.

1. On the PK sampling days, duvelisib will be administered in clinic in the morning after predose PK sampling.

2. An additional blood sample(s) for PK is requested at the start and end of any drug interruptions for an AE, when feasible.

3. PK blood samples will be collected from all patients on C1D1 and C1D15 at predose (within 30 minutes prior to the morning dosing) and 0.5, 1, 1.5, 2, 3, 4, and 6 hours postdose.

4. Predose sample is drawn within 30-minutes prior to the morning dosing.

5. PK blood samples will be collected only from patients receiving 50 mg BID on C2D15 at predose (within 30 minutes prior to the morning dosing) and 0.5, 1, 1.5, 2, 3, 4, and 6 hours postdose.

6. PK blood samples will be collected from all patients on C1D15 and C2D15 at predose (within 30 minutes prior to the morning dosing) and 1, 2, and 4 hours postdose.

# LIST OF ABBREVIATIONS

Abbreviation	Definition
 FDG-PET	[  F] Fluorodeoxyglucose-positron emission tomography
5PS	5-point scale
AE	Adverse event
ALC	Absolute lymphocyte count
ALCL	Anaplastic large cell lymphoma
ALT	Alanine aminotransferase
AST	Aspartate aminotransferase
BID	Twice daily
CEC	Central ethics committee
CMV	Cytomegalovirus
CR	Complete response
CRO	Contract Research Organization
CT	Computed tomography
СХ	Cycle X
СҮРЗА	Cytochrome P450 3A
DCR	Disease control rate
DNA	Deoxyribonucleic acid
DOR	Duration of response
DX	Day X
ECG	Electrocardiogram
ECOG	Eastern Cooperative Oncology Group
eCRF	Electronic case report form
EOT	End-of-Treatment
FDA	Food and Drug Administration
GCP	Good Clinical Practice
G-CSF	Granulocyte-colony stimulating factor
Gi	Giga (1 x 10  ) or 1 billion
GI	Gastrointestinal
HBcAb	Hepatitis B core antibody
HBsAg	Hepatitis B surface antigen
HCV Ab	Hepatitis C Ab
HIV	Human immunodeficiency virus

Abbreviation	Definition
HSV	Herpes simplex virus
HTLV-1	Human T-lymphotropic virus type 1
IB	Investigator's Brochure
ICF	Informed consent form
ICH	International Council for Harmonisation
IEC	Independent ethics committee
Ig	Immunoglobulin
IHC	Immunohistochemistry
IRB	Institutional review board
IRC	Independent Review Committee
ITT	Intent-to-treat
IV	Intravenous(ly)
IWG	International Working Group
LDi	Longest transverse diameter of a lesion
LVEF	Left ventricular ejection fraction
MedDRA	Medical Dictionary for Regulatory Activities
MRI	Magnetic resonance imaging
NCI CTCAE	National Cancer Institute Common Terminology Criteria for Adverse Events
NKTL	Natural-killer/T-cell lymphoma
NOS	Not otherwise specified
ORR	Objective response rate
OS	Overall survival
PD	Progressive disease
PFS	Progression-free survival
P-gp	P-glycoprotein
PI3K	Phosphoinositide-3-kinase
РО	Oral(ly)
PPD	Cross product of the LDi and perpendicular diameter
PR	Partial response
PTCL	Peripheral T-cell lymphoma
QD	Once daily
QTcF	QT interval corrected with Fridericia's method
SAE	Serious adverse event

Abbreviation	Definition
sALCL	Systemic anaplastic large cell lymphoma
SAP	Statistical Analysis Plan
SCT	Stem cell transplantation
SD	Stable disease
SDi	Shortest axis perpendicular to the LDi
SPD	Sum of the product of the perpendicular diameters for multiple lesions
SPTCL	Subcutaneous panniculitis-like T-cell lymphoma
SUV	Standardized uptake value
TEAE	Treatment-emergent adverse event
ULN	Upper limit of normal
US	United States
UV	Ultraviolet
VZV	Herpes zoster virus
WBC	White blood cell count
WCBP	Women/woman of childbearing potential
β-hCG	β-human chorionic gonadotropin

# 1. BACKGROUND AND STUDY RATIONALE

# 1.1. Peripheral T-cell Lymphoma

Peripheral T-cell lymphoma (PTCL) is a rare, aggressive type of non-Hodgkin lymphoma with an incidence of < 1 in 100,000 in the United States (US). The incidence varies geographically, with higher incidences in Asian countries than in Western countries (Park et al, 2014). PTCL generally affects people aged 60 years and older and is diagnosed slightly more often in men than in women. In addition to the incidence, there is a geographic difference in the PTCL subtypes. For example, PTCL-not otherwise specified (NOS) is the most common subtype in North American and Europe, while adult T-cell leukemia/lymphoma (ATLL) is most common in Asia (Vose et al, 2008).

Patients with newly diagnosed PTCL are most commonly treated with combination chemotherapy regimens, often followed by consolidation with high-dose chemotherapy and stem cell transplantation (SCT). However, the majority of patients develop relapsed or refractory disease (Zinzani et al, 2016). In addition, co-existing co-morbidities often preclude SCT consolidation in older PTCL patients.

Historically, patients with relapsed disease have had a dismal prognosis, with a median overall survival (OS) of less than 6 months. Pralatrexate, a folate analog, and belinostat and romidepsin, both intravenously (IV)-administered histone deacetylase inhibitors, were approved by the US Food and Drug Administration (FDA) for the treatment of relapsed or refractory PTCL patients based on objective response rates (ORR) ranging from 25% to 27% in single-arm studies. Brentuximab vedotin, a CD30-directed antibody-drug conjugate, also administered IV, is indicated for systemic anaplastic large cell lymphoma (sALCL), a sub-type of PTCL, also on the basis of a single-arm study. To date, no agent has been shown to improve OS. However, these treatments are associated with toxicities and only one to date is globally available (Laribi et al, 2018). Apart from a few patients who achieve complete response (CR), response durations remain brief. Therefore, PTCL remains a condition of high unmet medical need.

# 1.2. Duvelisib (IPI-145; VS-0145)

Phosphoinositide-3-kinase (PI3K) is a lipid kinase involved in intracellular signal transduction in many cells. The isoforms of PI3K's catalytic subunit (p110) exist as  $\alpha$ ,  $\beta$ ,  $\delta$ , and  $\gamma$ , the  $\delta$  and  $\gamma$  isoforms being preferentially expressed in leukocytes and involved in innate and adaptive immune function (Clayton et al, 2002; Okkenhaug et al, 2002; Vanhaesebroeck et al, 2010; Fung-Leung et al, 2011). For patients with advanced hematologic malignancies, including T-cell lymphomas, the pathways mediated by PI3K- $\delta$ , $\gamma$  contribute to survival, proliferation, and differentiation of cancer cells. It is well recognized that cancer cells, through the expression of various cytokines, growth factors, and chemokines, recruit multiple cell types, including myeloid cells capable of differentiating into tumor-associated macrophages that promote angiogenesis and augment tumor growth (Lewis et al, 2006). PI3K- $\delta$  and PI3K- $\gamma$  also have roles in the establishment and maintenance of the tumor microenvironment that plays an important role in

the development and maintenance of cancer cells (Hanahan et al, 2011). Accordingly, PI3K- $\delta$ , $\gamma$  inhibition would be expected to disrupt tumor maintenance and progression (Schmid et al, 2011).

Duvelisib is a potent PI3K- $\delta$ ,  $\gamma$  inhibitor being developed by Secura Bio, Inc. (Secura Bio) as an orally administered therapeutic in hematologic malignancies, including PTCL. Duvelisib is mechanistically distinct from other agents either currently available or being developed for PTCL and has demonstrated encouraging clinical activity in heavily pre-treated PTCL patients treated at doses of 60 mg twice daily (BID) (n = 2), 75 mg BID (n = 13), or 100 mg BID (n = 1). Among these 16 patients, the Investigator-assessed ORR per International Working Group (IWG) criteria was 50% (8/16), which included 2 CRs and 5 partial responses (PRs) in the 75 mg BID dose group and 1 CR in the 60 mg BID dose group. Responses were seen across the spectrum of PTCL subtypes, with CRs in patients with enteropathy-associated T-cell lymphoma (EATL), angioimmunoblastic T-cell lymphoma (AITL), and PTCL-NOS, and PRs in those with subcutaneous panniculitis-like T-cell lymphoma (SPTCL), ALCL, AITL and PTCL-NOS. Responses were observed in patients who had relapsed from prior treatment with approved therapies for PTCL. The median time to response was 1.9 months and the median duration of response was not estimable, as only 1 patient had progression or death after response. The median OS was 8.4 months, and the estimated probability of survival at 24 months was 34.4%.

Furthermore, duvelisib demonstrated an acceptable safety profile in this relapsed and refractory patient population. In the combined population of patients with PTCL or cutaneous T-cell lymphoma (n = 35), the most frequently observed  $\geq$  Grade 3 adverse events (AEs) were elevated transaminase (11 patients; 31% alanine aminotransferase [ALT]/aspartate aminotransferase [AST]), maculopapular rash (6 patients;17%), neutropenia (3 patients; 9%) pneumonia (5 patients;14%), and lung infection (3 patients; 9%), which were generally manageable with dose modifications and standard of care interventions (Horwitz et al, 2018).

For additional preclinical information on the antitumor activity of duvelisib, please see the Investigator's Brochure (IB).

# **1.3.** Study Rationale

The activity and evidence of response durability in 16 patients with heavily pre-treated PTCL observed in the Phase 1 study suggest that duvelisib is an active single agent for relapsed or refractory PTCL, an indication with a high unmet therapeutic need.

The Phase 2/3 clinical dose of duvelisib has been identified as 25 mg BID for patients with indolent non-Hodgkin lymphoma and chronic lymphocytic leukemia. Duvelisib (COPIKTRA™)

was approved in the US in September 2018 with a dosage of 25 mg orally BID and is indicated for the treatment of adult patients with relapsed or refractory CLL or SLL after at least two prior therapies and accelerated approval for the treatment of adult patients with relapsed or refractory FL after at least two prior systemic therapies. In the Phase 1, dose-escalation study in patients with hematologic malignancies, including PTCL, duvelisib was administered BID at escalating doses of 8 mg, 15 mg, 25 mg, 35 mg, 50 mg, 60 mg, 75 mg, and 100 mg, with the maximum

tolerated dose identified as 75 mg BID. Patients with PTCL received dose levels  $\geq$  60 mg; therefore, the activity of duvelisib in patients with PTCL at lower dose levels has not been evaluated. Accordingly, the current study will employ a Dose Optimization Phase, in which patients will initially start treatment with duvelisib 25 mg BID, with potential sequential escalation on a per-patient basis to 50 mg BID and then 75 mg BID, based on disease response and tolerability. The optimal dose, as identified in the Dose Optimization Phase will then be selected for use in the subsequent Expansion Phase.

As described in Section 11.13 a review of preliminary indications of response in each cohort was conducted when 5 patients had completed the first cycle in each cohort of the Dose Optimization Phase. Responses had been reported by the investigators for at least one patient in each cohort and enrollment was allowed to continue.

The interim analysis from the Dose Optimization Phase demonstrated the following:

- Sixteen patients on Cohort 1 and 11 patients on Cohort 2 received at least one dose of duvelisib. Ten patients from each cohort were evaluable for response. Six patients discontinued treatment prior to reaching the first assessment, all of whom were on Cohort 1. Premature discontinuations were due primarily to disease progression and/or toxicities.
